9.3 Research procedures

Research activities will include a baseline interview and follow-up interviews at 4 weeks and 3 months; all interviews will be conducted over the phone. Patients in the intervention arm will receive a prompt to call into an interactive voice response (IVR) system one day after their baseline interview (so 2-45 days after their index clinic visit) to confirm understanding and safe use of their medicine (described in 9.2 Description of the Intervention).

Pilot Testing. We will pilot-test the study battery, protocol and patient materials among English and Spanish-speaking patients at Alliance sites. Cognitive interviews will be conducted among a convenience sample of 30 patients (n=15 per language) that meet full eligibility criteria. We will obtain average interview completion times, elicit patient comprehension, and acceptability of the interview and patient materials. Any identified problems will be analyzed and modifications made as appropriate. Pilot patient data will be used if no significant changes are made to the study.

STU#: 00201638

Initial Interview. After confirming patient eligibility, obtaining verbal consent, and receiving patient prescription information, the RA will administer the baseline interview via phone. As long as the patient is still taking or planning to take the prescribed medicine, the patient will then be eligible for follow-up interviews and, if in the intervention arm, to receive the remaining EMC2 components (IVR, nurse follow-up).

Follow-up Interview #1. The first follow-up interview will be scheduled at the time of the baseline interview for 4 weeks later.

Follow-up Interview #2. The second follow-up interview will be scheduled at the time of the 4-week interview for 8 weeks later.

Spanish Language Materials. All study materials (screener script, consent form, battery, IVR call) have been or will be translated into Spanish to accommodate Spanish speakers. Several of the measures in the battery already have validated Spanish versions; everything else has been translated by Research Support Services, led by [name], using a modified committee approach. In this translation approach, three bilingual, bicultural translators independently translate one-third of each document into Spanish, then discuss the resulting texts and reach an agreement on best words/phrases for the final product. The strength of this approach has been recognized by the Census Bureau Guidelines for Survey Translation.

Provider Survey: We will send brief surveys to providers via email from the intervention clinics toward the end of the study to collect data about their experience with the tools. We will also have the provider survey available in a pen and paper version in the event that the Northwestern research team can attend an in-person provider meeting.

9.4 Data Sources

Data sources for this study will include phone interviews with participants, data from participant responses to the IVR call, and survey responses from providers.

Data collected. The following measures, including covariates, effectiveness and fidelity outcomes, are described below.

Patient Covariates. Baseline assessment will include socio-demographics, social support, English proficiency, country of origin, health status, including number of comorbidities, and cognitive function (assessed by the Mini-Mental Status Exam). We will also probe for medication concerns (i.e. about costs, side effects, risks) for patients who do not fill or are not taking their medicine. We will assess health literacy via the Newest Vital Sign (NVS). Patients are given a copy of a nutrition label and asked 6 questions about how they would interpret and act on the information. Scores are classified as high likelihood of limited literacy (0-1), possibility of limited literacy (2-3), and adequate literacy (4-6). The NVS has a high correlation with the Test of Functional Health Literacy in Adults (TOFHLA) takes less time to administer, is validated in Spanish and includes numeracy items.

Patient Motivation. The Consumer Health Activation Index (CHAI) assesses participants' 'activation' or motivation to participate in healthcare decisions and actions.

Effectiveness Outcomes: Medication Knowledge. Medication-specific knowledge measures will be created per high-risk medication. Similar items will be made standard across drugs, related to 1) decision making prior to use, 2) risks and benefits, and 3) side effects. Correct answers will be

STU#: 00201638

tailored to the available content included in each Med Guide Summary, as done previously by our team. Total scores range from 0-100, calculated reflecting the % correct of total possible points for each medication.

Medication Behavior. We will assess medication behavior by three domains: fill, proper use, and actual use.

- Fill will be assessed by patient self-report (yes/no) of having attained the medication from the pharmacy.
- Proper Use, measured as yes/no per medication, will be assessed by requiring patients to properly indicate the correct indication, dose (# pills each time), frequency (times per day), and total pills per day.
- Adherence will be measured via the ASK-12 that includes 12 items assessing general medication attitudes and beliefs as well as, specific behaviors within the past 3 months.

Adverse Drug Events (ADE). ADEs will first be assessed using a validated questionnaire administered by the RA during the 3-month follow-up phone call. If the patient reports that their medication is finished at the 1-month interview, the ADEs will be assessed using the same approach at the 1-month interview. [name] will review all self-reported ADEs to determine whether these symptoms could reasonably be linked to one of the prescribed high-risk medications. We will then determine whether confirmed ADEs were reported to the clinic via the IVR system by reviewing IVR data. Drs. [name] and [name] will oversee this process.

Fidelity Outcomes:

- Provider Counseling. We will ask patients (yes/no) whether their prescriber/nurse/pharmacist counseled them. We will also ask the Health Literacy supplemental items of the Consumer Assessment of Health Providers Survey (CAHPS) to evaluate the extent and quality of provider verbal counseling on Rx medications. Prescriber/nurse counseling will be assessed immediately following the appointment (during the baseline interview); pharmacist counseling will be assessed at baseline if the prescription has been filled by that time, otherwise on the 4-week call.
- Receipt of Med Guide Summaries. We will ask patients in both arms whether they received any written information from their provider.
- Receipt of IVR Calls and Nurse Counseling. We will collect data from the IVR to determine whether interviews were completed and whether responses warranted nurse counseling.
- Frequency of Clinic Follow-Up. We will ask patients (yes/no) whether someone from the clinic contacted them following any concerns reported to the IVR system.
- Helpfulness of EMC2 components. Intervention patients will be asked (yes/no) whether they received Med Guide Summaries, IVR calls, and follow-up nurse calls and how helpful they were. "On a scale of 1 to 10, 1 being not helpful at all and 10 being extremely helpful, how helpful was...?"
- Provider experience. We will ask providers at intervention clinics about their use of the BPA pop-ups (if they saw them and if so, how they used them), med sheets (if they noticed patients receiving them), and IVR (if they received any feedback from the patients about the call and if they saw any of the IVR reports).

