7. STUDY TIMELINES

An individual patient subject will be involved in the study for a total of up to 3 months. They will complete a screener enrollment interview, a baseline interview as soon as possible following the screener, a possible follow-up interview at 4 weeks, and a possible final interview at 3 months. The need for follow-up interviews will be determined by a patient’s medication fill and take behavior (if they do not plan to fill or take the medicine or have already stopped taking the medicine, we will not need to continue with follow-up interviews). All interviews will be conducted over the phone.

We anticipate that patient enrollment will actively take place over 2 years. The date by which we expect to complete primary analyses is August 31, 2019.

Our proposed/anticipated study timeline is below:

Table 2. Study Timeline TASKS	Y1				Y2				Y3				Y4	
	1	2	3	4	1	2	3	4	1	2	3	4	1	2
PREPARATION PHASE:														
Organize research team, convene DSMB	■	■												
Translate study materials	■	■												
Protocol development	■	■												
Prepare and refine EHR tools	■	■												
Prepare and refine IVR tools	■	■												
Site orientation, training, logistics planning				■										
Prescriber randomization				■										
Integrate, pilot, debug EMC ²				■										
IMPLEMENTATION PHASE:														
Implement EMC ² Strategy				■										
Recruit, consent participants				■	■	■	■	■	■	■	■			
Conduct baseline interviews				■	■	■	■	■	■	■	■			
Conduct 2 week and 3 month interviews				■	■	■	■	■	■	■	■			
Seek process feedback from clinical staff				■			■						■	
EVALUATION PHASE:														
Clean & analyze data						■	■	■	■	■	■	■	■	■
Summarize and interpret findings								■	■	■	■	■	■	■
Provide feedback to sites, review scalability								■					■	■
Submit manuscripts for publication								■					■	■
Present findings at national venues								■	■				■	■

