8. STUDY ENDPOINTS

8.1 Primary and secondary study endpoints.

The study’s primary endpoints are medication knowledge and medication behavior (fill, proper use, and actual use).

8.2 Primary or secondary safety endpoints.

The study’s safety endpoints include assessment of any Adverse Drug Events (ADE).

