9.1 Study design

We will conduct a 2-arm, randomized trial at one Alliance-affiliated federally qualified health center (FQHC) in Chicago, Near North Health Services Corporation, to evaluate the EMC2 intervention strategy compared to usual care.

We will assess patients' Rx knowledge and behavior at baseline, 4 weeks, and 3 months. Prevalence of ADEs and rate of their detection will be determined at 3 months or at an earlier interview if they state having already completed the course of medication. The fidelity and economic impact of the intervention will also be investigated via process and cost measures, in addition to patient and provider feedback. Results will determine effectiveness and identify any necessary modifications, guiding future dissemination efforts.

Study Arms:

Usual Care. Current usual care includes 1) variable physician and/or nurse counseling without any EHR notifications or counseling support; 2) no distribution of print medication information materials in Alliance clinics, and variable, limited distribution likely in pharmacies; 3) no active surveillance of medication use post-visits.

Intervention Arm: EMC2 Strategy. Following a patient's movement through a provider visit at one of the Near North clinics randomized to the intervention, the following five activities (described in more detail in 9.2) will occur:

- Provider counseling (prompted by provider medication alert)*
- Automated delivery of med guide summary*
- IVR follow-up phone assessment
- IVR lab report to clinic via EHR
- Nurse counseling (if warranted by lab report)

**Because the first two activities must occur at the time of the clinic visit, which is before we will have the opportunity to invite the participant to enroll in the study, those activities will occur for all patients prescribed a study medication at an intervention clinic, regardless of whether or not they subsequently enroll. (see last paragraph of 3.1)*

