9.2 Description of the intervention

1. Provider Medication Alert: If a prescribing clinician attempts to place a new order or change an existing prescription for one of the study medications (Table 1), an EHR-generated alert will notify the provider that the medication requires patient counseling. This alert will contain a brief description of the top risks or side effects that patients may experience while taking this medication; this information is directly derived from the FDA-approved Medication Guide for the drug. The pop-up will also include an html link to the 1-page Med Sheet, which they can use to further inform their counseling.

2. Automated Delivery of Med Guide Summary: When the patient leaves an encounter and checks out, the medication order in Centricity will automatically cue printing of the 1-page Med Guide Summary.

STU#: 00201638

3. IVR Follow-Up Phone Assessment: One day after a patient's baseline interview (which will occur within 1-30 days post-visit), the patient will be prompted to call into the automated IVR system. The goal of the IVR call is to confirm patients' understanding and safe use of the prescribed high-risk medication they are taking, and to screen for any adverse drug events that may arise from having taken the medicine.

The call will investigate content areas that will be standard across all medications under study: 1) medication recognition, 2) medication fill (and fill barriers, if applicable), medication adherence (and adherence barriers, if applicable), perceived effectiveness, and side effects experienced. The IVR content was derived from the Med Guide Summaries. Patients are able to speak their responses as "yes", "no", or "do not know" or use their keypad.

To facilitate the call, patients will be sent (via text or phone call) a call-in number for the IVR system so that they are able to make the call at their convenience. The text with the call-in number will be sent on the day following the patient's baseline interview. (The day lag is needed so that the participant's medication data can first be uploaded to the IVR system in preparation for the call).

If subjects have not used the system after one day, a reminder text message, again including the call-in number, will be sent by the RA at Northwestern. If subjects have not used the system after two days, the RA at Northwestern will call the patient to remind them to call into the system and to ensure they have the call-in details.

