To account for the correlated nature of the data from participants at the same practice and multiple observations per patient, we will use GLMMs for analyses of all data, specifying identity link for continuous and the logit link for binary outcomes using PROC GLIMMIX in SAS (v.9.4). Treatment assignment by time will be the independent variable of primary interest and modeled as a fixed effect and practice location as a random effect, with additional subject statement to model correlations within patient. We will also include fixed effects for any potential confounding covariates noted in the descriptive studies. For all GLMM analyses we will report point estimates and 95% confidence

STU#: 00201638

intervals, and the extent to which random effects suggest correlation of outcomes within practice location. Additionally, we will estimate the ICCs for all outcomes to be used in future studies.

Aim 2 Analysis Plan: We will repeat all GLMM analyses described in Aim 1, but with the inclusion of a fixed effect for participants' literacy defined as limited (inadequate or marginal literacy) vs. adequate. We will formally test for differences in intervention effects according to literacy by including a literacy-intervention interaction term. Statistically significant interaction terms ($p < 0.05$) will indicate that the disparities in understanding between the intervention and usual care group vary by literacy level. Similar analyses will be used to test for interactions of intervention effects by age and English proficiency (using Census criteria of 'very well' vs. 'less than very well').

Aim 3 Analysis Plan: Following completion of enrollment, we will determine the extent to which the intervention was implemented as planned in the intervention arm. We will ask patients in the intervention arm if they were counseled, and whether they received the Med Guide Summaries and the post-visit IVR call. Bivariate analyses will be performed to compare relevant outcomes for H4-H7 between arms using t-tests, Wilcoxon Rank-Sum, or χ^2 tests, as appropriate. Aim 3 findings will also directly inform follow-up qualitative investigations in Aim 4.

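### Fill, a primary endpoint, has no ever-filled rule, and patients who say they will not fill leave follow-up, so later fill comparisons are selected and can hide an in-clinic effect

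*Combined protocol and SAP*

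**What the plan says.** - **Status.** Section 8.1 gives as primary endpoints "medication knowledge and medication behavior (fill, proper use, and actual use".
- **Definition.** Section 9.4: "Fill will be assessed by patient self-report (yes/no) of having attained the medication from the pharmacy". No day, denominator or rule for combining interviews is given.
- **Timing.** Section 9.1 assesses "Rx knowledge and behavior at baseline, 4 weeks, and 3 months". Section 9.2 places the baseline interview in a window, "which will occur within 1-30 days post-visit". Section 9.3 puts the IVR prompt one day after baseline at 2-45 days, which implies baseline on days 1-44. Section 9.4 (Provider Counseling) expects that some prescriptions will be unfilled at baseline.
- **Who is followed.** Section 7: "if they do not plan to fill or take the medicine or have already stopped taking the medicine, we will not need to continue" with further interviews. Section 9.3: "As long as the patient is still taking or planning to take the prescribed medicine, the patient will then be eligible for follow-up interviews". A patient who has not filled but intends to is therefore asked again; a patient who says they will not fill is not.
- **Order of events.** Provider counselling and the Med Guide Summary come before baseline (9.1). The IVR call, which asks about fill and fill barriers, comes after it (9.2).
- **Analysis.** Section 11.1 names proper use and adherence as the use outcomes and does not list fill. Fill enters only through the general statement covering all data, under which "Treatment assignment by time will be the independent variable of primary interest and modeled as a fixed effect", with a logit link for binary outcomes.

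**The concern.** Obtaining a newly prescribed drug is an event that happens once and is not undone. Asking about it repeatedly and modelling arm by time causes two problems.

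First, a baseline 'no' can mean 'not yet' or 'never', and the mix depends on how many days after the visit the interviewer reached the patient.

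Second, patients whose 'no' is best known, because they say they will not fill, leave the follow-up data on account of that answer. They leave after randomisation and after the in-clinic components, which could themselves change filling: a risk warning may deter it and counselling may encourage it. A follow-up comparison among those who remain is not a comparison of the randomised groups.

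At stake is whether the trial can report correctly on one named component of a primary endpoint, and whether the definition of fill is settled before the data are seen.

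**Working it through.** The plan gives no fill rate, fill effect or fill power, so there is no figure to reproduce. All rates below are assumptions.

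**1. Follow-up selection.** At baseline let A = filled, B = not filled but planning to, C = not filled and not planning to (interviews end), with A + B + C = 1. Let c = share of B who later fill. Other losses, and patients who filled and then stopped, are ignored.

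- Fill observed at follow-up = (A + Bc)/(A + B)
- Ever-filled among all enrolled = A + Bc
- Ratio of the two = 1/(A + B) = 1/(1 − C)

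The inflation depends only on C: 1/0.85 = 1.18 when C is 15%, and 1/0.95 = 1.05 when C is 5%. If EMC2 changes C, the arms are inflated by different amounts.

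**2. An in-clinic effect on declared non-fill.** Assume A/B/C = 65/20/15% in usual care and 72/23/5% in EMC2.

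| c | Observed at follow-up, usual care v EMC2 | Ever-filled, usual care v EMC2 |
|---|---|---|
| 0.50 | 75.0/85 = 88.2% v 83.5/95 = 87.9% | 75.0% v 83.5% |
| 0.75 | 80.0/85 = 94.1% v 89.25/95 = 93.9% | 80.0% v 89.3% |
| 0.90 | 83.0/85 = 97.6% v 92.7/95 = 97.6% | 83.0% v 92.7% |

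A difference of 8.5 to 9.7 points vanishes at each c. With 600 per arm and a simple two-proportion test ignoring clustering, ever-filled rejects 95% of the time or more; the follow-up comparison rejects about 5% of the time.

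**3. Does the mixed model repair this?** It keeps the baseline 'no' and assumes later answers are missing at random. Taken at its simplest, that predicts group C's later answer from other baseline 'no' patients, all of them planners, who fill at rate c. Predicted later fill is then A + (B + C)c:

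- c = 0.50: 65 + 35 × 0.5 = 82.5% v 72 + 28 × 0.5 = 86.0%, a difference of 3.5 points against a true 8.5.
- c = 0.90: 65 + 35 × 0.9 = 96.5% v 72 + 28 × 0.9 = 97.2%, a difference of 0.7 against a true 9.7.

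This illustrates the assumption and is not a fitted model. It recovers part of the effect at best, because the true later value for C, if the stated intention holds, is 'no'.

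The arm-by-time term also misleads. In the c = 0.50 case the arms differ by 72 − 65 = 7 points at baseline and by −0.3 observed at follow-up. That looks like a fading effect, although the ever-filled difference has grown to 8.5.

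**4. An IVR or nurse effect on planners.** Assume A/B/C = 70/20/10% in both arms and c = 0.50 v 0.75. Observed: 80/90 = 88.9% v 85/90 = 94.4%. Ever-filled: 80% v 85%. This effect is visible at follow-up.

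**5. Baseline and interview day.** With 10% declared non-fill, 3% who plan but never fill, and an exponential time to fill with a 4-day median among eventual fillers, baseline 'yes' = 0.87 × (1 − 0.5^(day/4)): 14% on day 1, 61% on day 7 and 87% on day 30. With a 1-day median it still runs from 44% to 87%. In a separate calculation with 85% eventual fill and a mean time to fill of 2 to 10 days, the share of 'no' answers that are only 'not yet' is 78-84% on day 1, 15-74% on day 7 and 0-22% on day 30.

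**The case against.** A reader might infer that follow-up fill is near 100% in both arms whatever EMC2 does, and that non-fillers are never asked again. The documents support neither. Section 9.3 keeps patients who still plan to take the drug, and the IVR and nurse steps act on exactly that group. With A of 50-80% and C of 5-20%, observed follow-up fill runs from 53% (no planner fills) to 100% (all do). In the step 4 scenario the follow-up comparison has about 84-91% power (432-540 per arm), against 63% for ever-filled at 600 per arm. There the planned comparison does better.

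The baseline answer is not blind either. It comes after the in-clinic components. In a simulation with declared non-fill of 20% v 10%, baseline fill of 63.5% v 71.7% had about 86% power with 600 per arm.

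The item asks whether the drug has been obtained, so a 4-week 'yes' is already cumulative. Section 11.1 never states an analysis for fill, hypotheses H1 to H3 do not name it, and power is not set on it. The baseline day may also cluster early: lists arrive the morning after the visit, and section 29 calls for recruitment within the first week.

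All of this limits the size and reach of the point. It does not remove the selection. The declared non-filler's 'no' is still absent from follow-up, and no rule carries it forward. Early interviews make 'not yet' answers more common.

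**Conclusion.** The point holds in a limited form. Fill is a one-time event within a primary endpoint, without a cumulative rule. The stated stopping rule combined with the only model that reaches fill gives a selected follow-up comparison. It overstates fill by 1/(1 − C) and can hide or distort an effect of the in-clinic components on declared non-fill. In the assumed example, 8.5 to 9.7 points shrink to about zero.

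IVR and nurse effects on patients still planning to fill can be seen at follow-up. The baseline answer carries some in-clinic effect, but mixed with days since the visit. The claim that follow-up fill cannot differ between arms goes too far.

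Every size here rests on assumed fill rates, on taking a stated intention not to fill as final, and on ignoring patients who filled and then stopped. The quoted rejection rates ignore clustering by clinic and so are not the trial's actual power. This is more than a missing detail, because the text followed literally gives the selected comparison and a better score can be built from answers already planned.

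**What to change.** In sections 9.4 and 11.1, define fill as one outcome per patient and study medication: ever obtained by the 4-week interview.

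- 'Yes' at any interview up to then counts as filled.
- A patient whose interviews ended because they do not plan to fill counts as not filled, not as missing.
- A patient unfilled at baseline but planning to fill takes the 4-week answer.
- A planner lost before 4 weeks stays missing, handled by the multiple imputation in section 11.1 or a sensitivity analysis.

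Analyse with a logit mixed model with arm as the effect (no arm-by-time term) and clinic as a random effect, adjusted for days from the index visit to the interview. The adjustment matters because the 4-week interview floats too: baseline on days 1-30 puts it at about days 29-58 (30 + 28 = 58), or up to day 72 if baseline can fall on day 44. If the fill date is asked, a fixed day from the visit is cleaner. Reconcile the windows in 9.2 and 9.3. Do not interpret baseline fill alone without days since the visit.

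The cost is wording, plus one question if the date is added. Downsides: a stated intention not to fill is taken as final, fills after the 4-week interview are not counted, and power for an effect confined to planners is lower than in the follow-up comparison.

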1.2 Hypotheses

Related to Aim 1, we hypothesize that:

H1: Patients receiving the EMC2 intervention will have better understanding of medication risks than those in the control arm.

H2: Patients receiving the EMC2 intervention will demonstrate safer use of their medication than those in the control arm.

STU#: 00201638

H3: Adverse drug events will have a higher rate of detection for patients in the EMC2 intervention arm than in the control arm.

Related to Aim 3, we hypothesize that compared to usual care, patients receiving the EMC2 strategies will:

H4: Report higher rates of provider Rx counseling

H5: Report higher rates of receipt of print Rx information.

H6: Be more likely to communicate Rx questions.

H7: Report a greater frequency of clinic follow-up.

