11.2 Power analysis

The sample size for this study was based on comparisons of the primary outcome of medication knowledge between the two arms (i.e., usual care vs EMC2) at the 3-month interview. We expect

STU#: 00201638

participants in the usual care arm to score an average of 55.6 (SD=28.4) based on a previous study testing comprehension of the FDA standard Med Guides to those to be used in this study. Enrolling 1200 participants and estimating 80% retention at the follow-up interview (n=960, 480 per arm), we will have 80% to detect a minimum difference of 5.5 between the EMC2 and the usual care arm assuming a Type I error of 5%, assuming 100 patients per practice site enrolled at baseline and n=80 available at 3 month follow-up. This effect size was calculated based on an independent t-test with a variance inflation factor to account for the cluster-randomized design. An intra-class correlation coefficient (ICC) of 0.001 was used as we expect the clustering of practice site to have minimal influence on patient outcomes.

Usual care estimates for understanding of risks and demonstrated safe use outcomes were obtained from prior work. For subgroup analyses on these outcomes for Aim 2, we expect roughly 38% to have limited health literacy. Detectable differences at 3 months are based on estimates of 3 patients per provider with limited literacy and 5 with adequate literacy. Detection of ADEs is defined as the number of events recorded in the medical chart out of the total number reported by patients at the 3-month interview. In a study in which 20% of participants reported at least 1 adverse drug event, 35 of their 166 (21%) reported events were recorded in their medical chart. Therefore, the sample size calculation for this outcome was based on 21% of reported ADEs in 20% of our expected sample at 3 months (n=96 per arm, 3 patients per 32 providers, assuming an equal number of providers in each arm will have patients with no ADEs). We will be able to detect a minimum of 18.2 between the EMC2 and the usual care arm. For subgroup analyses by literacy, we assume 1 patient per provider with limited literacy and 2 with adequate literacy.

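### Section 9.4 leaves confirmation of ADEs to one reviewer's judgement without specifying that arm or clinic is withheld, and disagrees with section 11.2 on whether confirmed or reported ADEs form the H3 denominator

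*Combined protocol and SAP*

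**What the plan says.** H3 in section 1.2 is directional: "Adverse drug events will have a higher rate of detection for patients in the EMC2 intervention arm than in the control arm". Section 8.2 lists ADEs as the safety endpoint, and section 9.1 calls for both ADE prevalence and the rate of detection.

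Section 9.4 sets out three steps.

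1. Collection: "ADEs will first be assessed using a validated questionnaire administered by the RA during the 3-month follow-up phone call", or at the 1-month interview if the medication is finished by then.
2. Attribution: one named person "will review all self-reported ADEs to determine whether these symptoms could reasonably be linked" to a study drug.
3. Detection: "We will then determine whether confirmed ADEs were reported to the clinic via the IVR system by reviewing IVR data".

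Two named doctors oversee the process. The section gives no causality scale, second rating or agreement check. Masking is not mentioned here or anywhere else in the document.

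Section 11.2 describes detection differently, counting reports made at three months: "Detection of ADEs is defined as the number of events recorded in the medical chart out of the total number reported by patients at the" (the sentence ends by naming that interview). Section 11.1 names detection of ADEs as an Aim 1 outcome without choosing between the two descriptions.

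**The concern.** Whether a symptom is linked to a drug is a matter of judgement, and the answer decides which events count. Arm would be easy to see in an unfiltered record. Randomization is by clinic, section 3.2 names the three intervention clinics, and the screening data in section 3.1 carry the clinic name. Under section 9.4 only intervention patients are asked how helpful the EMC2 components were. The IVR prompt goes out the day after baseline (section 9.2), so IVR responses will usually exist well before the 3-month ADE interview.

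Two results are exposed. If the reviewer is stricter in one arm across the board, that arm's ADE prevalence falls. If the reviewer is stricter about events that the clinic did not learn of, events leave the denominator but not the numerator, and that arm's detection rate rises on a confirmed-event denominator.

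**Working it through.** **The plan's own figure.** Inputs from section 11.2: usual-care detection 21% ("35 of their 166 (21%) reported events were recorded in their medical chart"), "n=96 per arm, 3 patients per 32 providers", and "We will be able to detect a minimum of 18.2 between the EMC2 and the usual care arm", read as percentage points. The 5% type I error and 80% power are stated there for the knowledge outcome; I assume that they carry over and that the test is two-sided. With unpooled variance:

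d = (1.960 + 0.842) × √{[0.21 × 0.79 + p2(1 − p2)] / 96}, where p2 = 0.21 + d.

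This gives d = 18.18 points, or 18.20 with a design effect of 1 + (3 − 1) × 0.001 = 1.002. The stated 18.2 reproduces, and masking the reviewer would not change it.

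**The two descriptions side by side.**

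| | Section 9.4 | Section 11.2 |
|---|---|---|
| Numerator | Reported to the clinic through the IVR | Recorded in the medical chart |
| Denominator | Confirmed ADEs | All ADEs reported by patients |
| Does attribution affect the rate? | Yes | No |

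**Illustration 1: undetected events ruled out in one arm.** The 96 is 20% of 480, that is, patients with an ADE; I use it as an event count. Detected: 0.21 × 96 = 20.16. Undetected: 75.84. If a fraction x of the undetected events in one arm is additionally ruled unrelated, the rate is 20.16 / [20.16 + 75.84(1 − x)].

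| x (assumed) | Calculation | Rate | Shift (points) |
|---|---|---|---|
| 0.1 | 20.16 / 88.42 | 22.8% | 1.8 |
| 0.2 | 20.16 / 80.83 | 24.9% | 3.9 |
| 0.3 | 20.16 / 73.25 | 27.5% | 6.5 |

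The largest shift is 6.5 / 18.2 = 36% of the stated detectable difference. The calculation combines a 21% chart-based rate from section 11.2 with the confirmed denominator of section 9.4, a pairing that the plan never states.

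**Illustration 2: uniform strictness in one arm.** If 20% of all events are ruled out whether or not they were detected, 76.8 remain, of which 16.13 are detected. The rate stays at 21%, but prevalence (one event per patient) falls from 96 / 480 = 20% to 76.8 / 480 = 16%. Bias in detection therefore needs attribution to vary with detection status or something related to it. Bias in prevalence needs only knowledge of arm.

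**Illustration 3: false-positive rate.** Assume 120 reported symptoms per arm, 21% detected in both arms, independent events, and 80% confirmed, except that undetected symptoms in the EMC2 arm are confirmed less often. The expected EMC2 rate is 0.168 / (0.168 + 0.79c), where c is the confirmation probability for undetected EMC2 symptoms. In 40,000 simulated trials per row, a two-sided 5% test of two proportions rejected as follows.

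| c (assumed) | EMC2 rate | Rejections with no true difference |
|---|---|---|
| 80% | 21.0% | 4.8% |
| 70% | 23.3% | 7% |
| 60% | 26.2% | 13% |
| 50% | 29.8% | 26% |

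**The case against.** A reader might infer that the reviewer knows the arm. The documents do not say so: they never mention masking, and silence does not show that it is absent. A reader might also take the reviewer to be a member of the study team. That is plausible, but the name is removed and no role is visible.

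A reader might further infer that attribution fixes the H3 denominator outright. Section 11.2 contradicts this, because its denominator is every event that patients report. On that definition, the first and third illustrations do not apply.

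Section 9.4 also offers some protection. The IVR check comes after attribution, IVR responses are captured in a separate database at the Boston site (section 10.1), and two doctors oversee the work. If that order is kept, the reviewer does not know which events the IVR flagged, and the second illustration shows that knowledge of arm alone need not move the detection rate. This stands as a limit on the size of the concern. But the order is only implied, nothing bars earlier sight of IVR data, and arm and clinic are not covered at all.

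Finally, the IVR numerator is zero in usual care by construction, so under section 9.4 the arms cannot be compared on detection, however attribution is done. That problem is separate and at least as serious. ADEs are also not among the primary endpoints in section 8.1.

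**Conclusion.** The point holds as a gap in specification. Attribution rests on one person's judgement, nothing specifies that arm or clinic is withheld, and clinic reveals arm. The result feeds ADE prevalence and, under section 9.4, the set in which detection is checked. Sections 9.4 and 11.2 disagree on the denominator and must be reconciled.

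The size cannot be known from the documents, which give no rate of differential attribution. On the assumed 10% to 30%, the detection rate moves by 1.8 to 6.5 points, with the 96 patients treated as events and a denominator that section 11.2 does not use. These figures show what could happen; they do not estimate an actual bias. The documents do not support a claim that the reviewer is unmasked, or that attribution sets the H3 denominator under every definition in the plan. The point is worth fixing because the remedy is so cheap.

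**What to change.** - Give the same reviewer a listing of symptom, drug, dates and reported timing only, without arm, clinic or IVR data. Remove any mention of these from free text.
- Lock the attribution with a date before IVR or clinic data are linked. This makes binding the order that section 9.4 implies.
- State in sections 9.4, 11.1 and 11.2 whether the H3 denominator is confirmed or reported ADEs.

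The cost is a filtered REDCap listing, a dated lock and a short text amendment, with no extra staff and no change to the sample size.

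The numerator must be settled separately. IVR reports arise in one arm only, and the chart entries that section 11.2 counts lie in records that section 25.3 puts out of the team's reach. Masking the reviewer cures neither problem.
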